1.5 Conduct of Study: Emory University, Office of Clinical Research

The protocol team at Emory receives guidance from the Emory Office of Clinical Research (OCR) in the design of protocol-related documents including Standard Operating Procedures, Data Management Plan, and Clinical Quality Management Plan. The OCR also provides guidance for clinical coordination and regulatory management, helping to ensure compliance with Good Clinical Practice (GCP), Emory University Institutional Review Board (IRB), US Food and Drug Administration (FDA), and other regulatory agencies (e.g., the OHRP) and NIAID/DAIDS (the Sponsor). Further information about the Emory OCR is found at: <https://www.ocr.emory.edu/>

1.6 Conduct of Study: Georgia Clinical & Translational Science Alliance (CTSA), Georgia CTSA Clinical Research Center (GCRC)

The study will be carried out using facilities of the Georgia CTSA GCRC located within the Emory University Hospital Clinical Research Site, with personnel based in the GCRC Nursing Staff and Core Laboratory.

<http://georgiactsa.org/discovery/clinical-sites/emory-university.html>

<http://georgiactsa.org/discovery/nursing.html>

Please see protocol Appendix [Section 17.3](#) for further details.

1.7 Conduct of Study: Emory University Investigational Drug Service

The pharmacy that will serve the study is the Emory University Investigational Drug Service (IDS) - <http://www.ocr.emory.edu/ids/index.html>

The IDS is currently involved in a number of NIAID/DAIDS studies, demonstrating the capacity of IDS to initiate, conduct, participate in, and support NIAID/DAIDS funded research. Please see Protocol [Section 17.4](#) for required IDS information.

1.8 Conduct of Study: Emory Medical Laboratory (EML)

Standard medical laboratory tests will be conducted by the Emory Medical Laboratory (EML).

The EML is a fully accredited and licensed clinical laboratory. EML participates in the College of American Pathologists (CAP) Laboratory Accreditation Program and has CLIA (Clinical Laboratory Improvement Amendments) certification through CMS (Centers of Medicare and Medicaid Services). Emory Medical Laboratory also is licensed by the state of Georgia.

EML Lab Reference Ranges and CLIA certificate are found at the website.

<http://www.emoryhealthcare.org/centers-programs/medical-laboratory/index.html>

1.9 Protocol Review, Finalization, and Approval Processes

The protocol will undergo a review, approval and set-up phase with the Georgia CTSA GCRC during the first 2 months of funding, as well as the Protocol Registration process with NIAID/DAIDS. A protocol-specific Manual of Operational Procedures in accordance with NIAID/DAIDS requirements will also be prepared and approved during this timeframe, incorporating procedures needed for this study and existing SOPs from the Winship CTO, Georgia CTSA GCRC and Core Lab, IDS Pharmacy, and Emory University Medical Laboratory.

2 Study Objectives

The overall objective of the study is to determine safe and immunologically effective doses of imatinib that will subsequently be advanced to future studies. Given toxicity of imatinib when given at 100mg with rifabutin and isoniazid, the objectives are amended to focus on evaluating potential beneficial effects of imatinib when given alone. If beneficial effects are seen, drug-drug interactions with relevant anti-tubercular therapies will be evaluated in future trials.

2.1 Primary Objective

- To determine the effects of different doses of imatinib on myelopoiesis in adults when given alone
- Primary Safety Objective: To determine the safety of different doses of imatinib in adults

2.2 Secondary Objectives

- To determine the effects of different doses of imatinib on *ex vivo* bacillary killing in adults when given alone
- To assess the PK and PD of imatinib in relation to myelopoiesis and *ex vivo* bacillary killing
- To determine the effects of imatinib on cellular immune function and on circulating biomarkers of immune activation and on T cells and monocytes
- To assess proteomic and transcriptomic changes associated with imatinib administration

3 Investigational Plan

3.1 General Design

This is an open label trial evaluating the safety, PK and immunologic effects (PD) of different doses of imatinib in healthy adult volunteers. In this revised protocol, 32 participants will be enrolled in a dose-escalating fashion to receive one of three imatinib doses alone for 28 days. Because 4 participants received imatinib at 100mg in a previous protocol, 8 participants will receive 100mg daily under this revised protocol, to complete dosing of 12 participants at 100mg imatinib daily. Safety evaluation to day 42 follow-up will be conducted for the first 6 participants in the 100mg stratum (4 previous participants, plus 2 more enrolled through this amended protocol) while the remaining 6 participants are continuing to accrue to the study. Once the safety evaluation for the first 6 participants is finalized, and enrollment of a total of 12 participants in the 100mg stratum is complete, we will begin enrolling 12 participants in the next

dose stratum (200 mg/daily). Enrollment will proceed in this fashion, with safety evaluation after the first 6 participants at each dose. In this manner, 12 participants will be allocated to each imatinib dose, proceeding from 100mg to 200mg and finally from 200mg to 400mg daily.

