Senior Scientific Officer, Tuberculosis Clinical Research
Branch Division of AIDS, NIAID, NIH, DHHS
[name]
Rockville, MD 20852
[contact]
E-mail: [contact]

PREFACE TO THIS AMENDED PROTOCOL:

In a previous version of this protocol that included imatinib dosing for 2 weeks, followed by imatinib together with rifabutin and isoniazid for another 2 weeks, we found 50mg imatinib to be the maximum tolerated dose when given with these drugs, and an unacceptably high rate of toxicity at imatinib 100mg when given as combination therapy. These data suggest further imatinib dosing with rifabutin and isoniazid should not be conducted at 100mg or higher. However, these data do not negate the potential of imatinib as a host-directed therapy for TB, as dosing at 100mg imatinib was safe when given alone during days 1-14. Our current goal is to determine if imatinib dosed alone has beneficial effects. If so, additional studies evaluating drug-drug interactions with agents other than isoniazid and rifabutin will be pursued. Hence, the amended protocol here is specific for volunteer studies using imatinib alone.

Imatinib Dosing Trial
Version: 5.0

SIGNATURE PAGE

Protocol Title: IMPACT-TB*: A phase II clinical trial of the safety, pharmacokinetics and hematologic effects of imatinib on myelopoiesis in adults when given with and without isoniazid and rifabutin

*Imatinib mesylate per oral as a clinical therapeutic for TB

DAIDS Protocol Number: Aim 1
DAIDS-ES ID 38518

DAIDS Protocol Version History:

Protocol Aim 1, Version 5.0, June 22, 2022

Protocol Aim 1, Version 4.0, September 13, 2021

Protocol Aim 1, Version 3.0, July 12, 2019

Protocol Aim 1, Version 2.0, March11, 2019

I will conduct this study in accordance with the provisions of this protocol and all applicable protocol-related documents. I agree to conduct this study in compliance with United States (US) Health and Human Service regulations (45 CFR 46); applicable U.S. Food and Drug Administration regulations; standards of the International Conference on Harmonization Guideline for Good Clinical Practice (E6); Institutional Review Board/Ethics Committee determinations; all applicable in-country, state, and local laws and regulations; and other applicable requirements (e.g., US National Institutes of Health, Division of AIDS) and institutional policies.

Investigator name	Signature	Date signed

Imatinib Dosing Trial
Version: 5.0

NIH Grant Number	NIH4UH3AI122320 - 03

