9.5.1 Study Progress and Safety Monitoring Plan

The Division of AIDS guidance on study monitoring have been implemented to develop a protocol-specific Study Progress and Safety Monitoring Plan (SPSMP), which will be approved

in writing by the assigned DAIDS Medical Monitor/Medical Officer before trial initiation. Briefly, the ISM, DAIDS representative, and the PI/study team will review all reports at least monthly, with AE reports generated every 2 weeks. The following reports will be generated: 1) Accrual update, 2) Progress report, 3) Delinquency report, 4) Periodic summary adverse event report, 5) Baseline characteristics report, 6) Data completeness report, 7) Outcomes summary report (completed, withdrew, etc), 8) Efficacy report (myelopoesis). The contents of the report will be as outlined in the DAIDS SPSMP protocol template, which can be found at: (https://www.niaid.nih.gov/sites/default/files/studydatamonitor_plan.pdf) and which has been used to create a study-specific SPSMP. The reports created for this process will be provided to DAIDS at the frequency of each review as specified in the SPSMP. The DSMB will receive these reports at the planned imatinib dose group 6- and 12- participant completion points as described in [Section 3.1.2.](#)

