The PI and the ISM will formally review clinical toxicity assessments with the DAIDS medical monitor every two weeks and after 6 participants have completed follow-up in a dose stratum. The PI and/or medical monitor will halt further enrollment at that dose level for formal review by the DSMB if any participant develops any emergent grade 3 or higher dose-limiting toxicity that is definite, possible or probable in causal relationship to the study drug, in the opinion of the PI. If no such toxicity is observed after the first 6 participants in a dose stratum have completed follow-up, and a total of 12 participants are enrolled in the first stratum, then the next dose stratum will be opened for enrollment.

The safety rationale for opening accrual to a higher dose level, based upon findings from the first 6 participants at the previous lower dose level, is as follows: Rather than use a standard 3 + 3 dose escalation design, we will utilize a more conservative threshold for halting accrual. In this study, enrolling healthy volunteers, a frequency of >33% grade 3 or higher dose-limiting toxicity attributed to a study drug would warrant formal review by the DSMB. We propose to protect participant safety by performing a safety analysis after 6 participants have completed the day 42 follow-up visit, a sample size that gives us greater than 90% power to identify a safety signal and halt accrual at that dose level, based upon a true rate of grade 3 or higher toxicity of 33% (or greater).

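### The stated >90% power of the six-participant safety look is not assured for 28-day imatinib alone at 100 mg, and Section 8.1.2 is inconsistent on when the pre-400 mg review takes place

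*Combined protocol and SAP*

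**What the plan says.** All references are to Version 5.0 unless stated.

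Section 9.5.1 plans a safety analysis once six participants at a dose have been followed to day 42. It describes this as "a sample size that gives us greater than 90% power to identify a safety signal and halt accrual at that dose level", taking a true grade 3 or higher rate of 33% or more, and draws no distinction between doses. Enrolment at a dose halts "if any participant develops any emergent grade 3 or higher dose-limiting toxicity" that is judged related to study drug.

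Section 3.1 defines the 100 mg group for this look as the "first 6 participants in the 100mg stratum (4 previous participants, plus 2 more enrolled through this amended protocol". Version 5.0 gives 28 days of imatinib alone. The earlier participants had imatinib alone for 14 days, then imatinib with isoniazid and rifabutin for 14 days (regimen in Version 3.0, Section 3.1.2). The Version 5.0 preface reports "an unacceptably high rate of toxicity at imatinib 100mg when given as combination therapy", and also that "dosing at 100mg imatinib was safe when given alone during days 1-14".

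For the step to 200 mg, Section 3.1 asks that the six-person evaluation be finalised and that "enrollment of a total of 12 participants in the 100mg stratum is complete". Section 9.5.1 similarly requires no such toxicity in the first six "and a total of 12 participants are enrolled in the first stratum". Section 3.1.2 extends the safety judgement to volunteers 7 to 12. Section 12.1 requires a DSMB recommendation before each new dose.

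Section 8.1.2 places the review before 400 mg after the first six at 200 mg reach the day 28 visit. Its next sentence says 42-day follow-up is needed for a participant to count toward the six.

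**The concern.** The power figure clears 90% by about one percentage point, and it needs six people who can each show toxicity of the regimen being judged. At 100 mg only two of the six take that regimen throughout. The other four stop being informative about imatinib alone after day 14, because anything later is confounded with rifabutin and isoniazid. The protocol does not say outright whether their events in that later period count toward the 100 mg criterion.

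This look helps decide whether healthy volunteers move from 100 to 200 mg. A review body relying on Section 9.5.1 would take it that a one-in-three rate of serious toxicity on imatinib alone would be caught more than nine times in ten, and that is not shown for this dose.

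The Section 8.1.2 wording concerns the review before the highest dose. Followed literally, its day 28 trigger would allow that review to start without the 14 days of post-drug follow-up.

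**Working it through.** **Inputs.** True rate p = 0.33, so q = 1 − p = 0.67; six participants; halt on one or more related grade 3+ events (Section 9.5.1). Composition at 100 mg is 4 + 2 (Section 3.1), with eight Version 5.0 participants planned at that dose. The share of 28-day imatinib-alone toxicity that arises by day 14 is not in the documents, so I vary it from 0 to 1.

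**Step 1: the plan's figure.** 1 − q^6 = 1 − 0.67^6 = 0.910 (0.912 if p = 1/3). Requiring two or more events in six would give only 0.642, so the any-event rule as written is what produces >90%. The figure is right for six people on one regimen.

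**Step 2: 100 mg, combination-period events of the four not counted.** Let s be the share of the 33% risk that arises by day 14. Each of the four contributes a risk of 0.33s and each of the two contributes 0.33:

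power = 1 − (1 − 0.33s)^4 × 0.67^2

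| s | Power |
|---|---|
| 0 | 55.1% |
| 0.25 | 68.2% |
| 0.50 | 78.2% |
| 0.75 | 85.6% |
| 1 | 91.0% |

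Setting power to 0.90 gives s ≈ 0.948, so about 95% of the toxicity must arise by day 14 to exceed 90%.

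If the share f is instead defined on the cumulative-hazard scale, power = 1 − q^(2+4f). The ends are the same. An assumed constant hazard over 28 days (f = 0.5) gives 1 − 0.67^4 = 79.8%.

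Section 12.1 does not settle the share. It places asymptomatic aminotransferase rises at 2 to 8 weeks, but says marked ALT rises usually appear only after 6 months.

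**Step 3: combination-period events counted.** Six people then contribute throughout and 1 − q^6 applies formally, but p is now the rate for a mixture of regimens. It is not the rate for 28 days of imatinib alone.

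**Step 4: replacements.** Section 3.1.2 replaces anyone among the first six who does not reach day 42. If k of the earlier four were replaced by Version 5.0 participants, the lower limit is 1 − q^(2+k): 69.9%, 79.8%, 86.5% and 91.0% for k = 1 to 4. The documents do not report k.

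**Step 5: all eight Version 5.0 participants followed before escalation.** 1 − q^(8+4f) runs from 1 − 0.67^8 = 95.9% (all toxicity after day 14) to 1 − 0.67^12 = 99.2% (all by day 14).

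**Step 6: Section 8.1.2.** Day 28 (trigger sentence) stands against day 42 (next sentence, Section 3.1.2 and Section 9.5.1). This does not alter the binomial figure for six participants. It alters how much of the toxicity window has been observed.

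**The case against.** The strongest reply is that nothing tells the reader to discard the four's later events. Section 3.1.2 reviews six people given 100 mg once they reach day 42, and asks about grade 3 or 4 events related to imatinib without limiting the period. The four were still taking imatinib 100 mg in days 15 to 28, and Section 9.3 of Version 3.0 assessed each drug taken for relationship. On that reading six people count in full, and including combination-period events makes a halt more likely, which is the cautious direction. That is a fair reading of the text. It does not restore the claim for imatinib alone, because the look then includes a combination the preface already calls unacceptably toxic.

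The second reply is that the six-person look is not the only gate. Volunteers 7 to 12 are considered, the any-event halt operates throughout, and "The DSMB will receive these reports at the planned imatinib dose group 6- and 12- participant completion points". The DSMB must also recommend each step. This stands, and it substantially lowers the practical risk. It does not make the power statement true at 100 mg: Sections 3.1 and 9.5.1 expressly require the later participants only to be enrolled, and Section 9.5.1 does not make the 12-participant report a condition for opening the next dose.

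Third, the lower figures rest on unknowns. That is correct, and it limits the conclusion to not assured. A reader might infer that the power at 100 mg simply is 55%. The documents do not support that: it requires both that combination-period events are ignored and that no grade 3+ toxicity arises by day 14. The preface's report that 100 mg alone was safe to day 14 does suggest that, under the not-counted rule, new information on imatinib alone would come only from the two added participants. But that is a statement conditional on data already seen, not the advance power that Section 9.5.1 describes.

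On Section 8.1.2, a reader might infer that the review is set at day 28 instead of day 42. The section's next sentence rules that out as a settled rule, since nobody would yet count toward the six at day 28. Day 42 is the evident intent.

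**Conclusion.** The arithmetic in Section 9.5.1 is correct, and the statement holds at 200 and 400 mg, where all six receive the regimen under review. It is stated too broadly for 100 mg. There, power for 28 days of imatinib alone is between 55.1% and 91.0% at a true rate of 33% if combination-period events are not counted. If they are counted, the figure describes a mixed regimen. Which case applies, and where in the range the first would fall, depends on a counting rule and a timing share that the documents do not give. The range also assumes that all four earlier participants remain in the six; any replacement raises its lower end.

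The documents do not show that an unsafe escalation to 200 mg is likely. With all eight Version 5.0 participants followed, detection would be at least 95.9%, and the other safeguards work alongside the six-person look.

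Section 8.1.2 contradicts itself on the pre-400 mg review. Both points should be corrected because each bears on a dose-escalation decision in healthy volunteers and the corrections cost almost nothing.

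**What to change.** **Section 9.5.1, one of two changes.**

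- Option A: limit the >90% statement to looks in which all six participants received the regimen under evaluation. Cost: one clause.
- Option B: base the 100 mg look on six of the eight Version 5.0 participants already planned, which gives 91.0%. Cost: some calendar delay before the look, with no added participants.

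**Section 3.1.2.** Under either option, add one sentence saying whether grade 3 or higher events in the four earlier participants during combination dosing count toward the 100 mg criterion.

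**Section 8.1.2.** Change the trigger from the day 28 visit to the day 42 visit, to agree with its own next sentence and with Sections 3.1.2 and 9.5.1. Cost: one number.

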3.1.1 Screening Phase

The in-person screening evaluations will occur on days -8 to 0. Upon arrival at the GCRC for the in-person screening visit, the participant's temperature will be taken and participants will be asked to provide written informed consent. If consent is provided, demographic and medical history and medical record review will be conducted and an HIV test will be performed. Testing for HBV and HCV will also be performed. Inclusion and exclusion criteria will be examined. For women of reproductive potential, a pregnancy test will be performed. Physical exam with vital signs, medication review, lab safety tests, urinalysis, and a 12-lead ECG will be performed. These activities may be spread over multiple visits within the indicated time window.

Participants who consent and who meet all of the inclusion criteria and none of the exclusion criteria will be enrolled.

3.1.2 Study Intervention Phase

The doses of imatinib used here are the same or lower than those used routinely and safely in CML patients, and we do not expect any Grade 3 or Grade 4 adverse events (AEs). Hence, safety evaluations for this imatinib-only amended protocol will consist of e-mailed adverse event reports to DAIDS, followed by communication from DAIDS to the DSMB. Any Grade 3 or Grade 4 adverse events will be reported to DAIDS in real time.

We will enroll using a sequential dose-escalation design. Specifically, we will enroll 2 more participants in the imatinib 100 mg qD arm, which brings enrollment in this group to 6 participants. We will conduct a safety review of adverse events after these 6 participants given imatinib 100mg complete day 42 follow-up. Enrollment of the second 6 participants in the 100mg dose group will continue while safety review of the first 6 participants is conducted by the DSMB via e-mail. The plan to continue enrollment during this review period is based on the known safety profile of imatinib in CML patients who take 400 to 800mg daily. If after the first 6 participants at 100mg complete the 42-day study follow-up there are no treatment emergent grade 3 or 4 adverse events considered to be related to imatinib treatment, and there are no serious adverse events or other safety concerns among these first six volunteers as well as volunteers 7 - 12 in the opinion of the investigators, the Independent Safety Monitor, the DSMB,

and the Sponsor that would prevent dose escalation (also documented through e-mail communication), we will commence enrollment of the 12 participants in the next dose group (200mg qD arm). We will again conduct a safety review of adverse events via e-mail after the first 6 participants in the group complete day 42 followup while continuing with the next 6 participants in the group as above, following the same procedures before starting the 400mg imatinib group. After 6 participants complete day 42 followup in the 400 mg qD arm, we will review safety data and PK/PD data while enrollment in the 400 mg/day group continues. If the safety criteria above are met, we will complete enrollment of remaining participants in the 400 mg qD arm. This approach will proceed until there are 12 participants with evaluable myelopoiesis data in each dose arm and the sample size of 48 participants (16 in the previous protocol version plus 32 in this version) is fulfilled. All enrolled participants will be evaluable for safety and toxicity assessments if they have taken at least one dose of a study drug. Note that in this protocol version, given imatinib dosing only occurs for 28 days, 42-day followup is required for a participant to “count” toward the 6 needed for followup assessment. Therefore, if any of the first 6 participants in a dose group do not complete the study to day 42, we will need to include other participants who complete the day 42 visit to fulfill the requirement. Similarly, because study endpoints require data collection up to day 14, if a participant drops out prior to day 14, we will enroll another participant to complete the required complement of 12 participants with protocol-compliant evaluable data (has taken $\geq 85\%$ of all doses of study drugs and completed visits to day 14) per dose group (see [Section 8.1](#) and [Section 8.2](#)).

After assignment to a group, each participant will be assessed for baseline data according to [Table 1](#) prior to their first imatinib dose. They will then take their first imatinib dose. Participants will then come back at various times during the 28-day period of imatinib-only dosing (see [Section 6](#) on Study Procedures). During this time, safety assessments will be performed and blood will be collected for lab assays. Participants will be given imatinib in pre-filled pill containers at visit 1 (day 1) as indicated on the schedule of events. There will also be an intensive PK study performed on day 14. On this day, participants will have an IV placed to minimize discomfort related to phlebotomy at repeated time-points after dosing. Participants will return to complete the last PK blood draw on day 15. Additional visits at days 21 and 28 will include safety and efficacy assessments. Volunteers will then discontinue all study drug and will complete one additional follow-up visit at day 42, 14 days after receiving their last dose, for safety.

Meal Timing for all participants: We will instruct participants to take drugs on an empty stomach. Our data on the first 16 participants dosed at 50 and 100mg of imatinib indicate that this results in expected PK exposures and is consistent with care of TB-infected patients, who are commonly instructed to take their anti-TB drugs after fasting. Breakfast may be eaten 1 hour after taking the study drugs. On study visit days, participants may eat a small breakfast at home at least 2 hours before the scheduled time of study drug administration (e.g. 7am), anticipating that the study drugs will be administered at the GCRC at 9am. On the PK study day (visit 4), a meal or snack will be provided 1 hour after study drug administration at the GCRC.

